3.2 Secondary Endpoints

The secondary endpoints are described below.

- The incidence of BPAR within the first 3 months, 3-6 months, 6-9 months, and 6-12 months after transplantation
- Time to achieve tacrolimus therapeutic range at 0 to 4 months (8-10 ng/mL)
- Proportion of patients who had dose adjustments and/or drug alteration or addition due to insufficient immunosuppression
- Incidence of acute and chronic renal impairment. Renal function will be assessed using estimated Glomerular Filtration Rate (eGFR). Creatinine clearance (CrCl) may also be calculated as a reference. Patients will be categorized as having either mild (eGFR of 60 mL/min/1.73m² to 89 mL/min/1.73m²), moderate (eGFR of 30 mL/min/1.73m² to 59 mL/min/1.73m²), or severe renal impairment (eGFR <30 mL/min/1.73m²).
- Incidence of adverse outcomes (ie, graft rejection, graft loss, renal impairment, adverse drug events, tacrolimus toxicities, and death)

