2.1 Background and Rationale

Renal transplantation from either a live or deceased donor has become the preferred treatment for patients with end-stage renal disease because it prolongs survival and improves quality of life (Port 1994; Schnuelle et al. 1998; Tonelli et al. 2011). Tacrolimus is the standard treatment for immunosuppression with kidney transplant patients as tacrolimus is associated with better graft survival and lower incidence of nephrotoxicity compared to cyclosporine (Bowman and Brennan 2008; Webster et al. 2005a; Webster et al. 2005b).

Tacrolimus is a good candidate for pharmacogenomic-guided dosing and monitoring as it displays variable pharmacokinetics and is also a narrow therapeutic index drug, whereby low drug exposure increases risk to kidney rejection and high doses correlate with nephrotoxicity (Birdwell et al. 2015; Hesselink et al. 2014; Provenzani et al. 2013). Reaching and maintaining therapeutic tacrolimus levels is also often problematic despite adjustment of the initial dose to body weight and frequent monitoring of tacrolimus levels. Furthermore, response to tacrolimus is dose-dependent with large intra- and inter-patient variability that has been partly attributed to genetic differences in the *CYP3A5* gene (Birdwell et al. 2015; Hesselink et al. 2014; Provenzani et al. 2013; Staatz, Goodman, and Tett 2010a, b).

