8.3 Statistical Methods

All analyses will be performed on the basis of the ITT principle. Unless stated otherwise, the term “descriptive statistics” will refer to the number of subjects, mean, median, standard deviation, minimum, and maximum for continuous data and to frequencies and percentages for categorical data. Categorical variables will be summarized as counts and percentages. All statistical parameters (eg, mean, median, standard deviation) will be tabulated together with their corresponding confidence intervals (CIs) and/or standard errors.

Continuous variables will be summarized as medians with first to third quartiles. Appropriate conventional statistical analyses will be used to assess the primary and secondary endpoints. Categorical data will be compared using χ^2 or Fisher’s exact test, as appropriate; some comparisons will require correction for potential confounders such as race/ethnicity; these will be performed using the Cochrane-Mantel-Haenszel test. Continuous variables will be compared using the Wilcoxon test or the t-test. The incidence of an adverse outcome (ie, graft rejection, graft loss, renal impairment, tacrolimus toxicities, and death) will be estimated using Kaplan-Meier curves. Depending on the distribution of the data, time-to-event (ie, time to reach therapeutic target range) analysis will be performed using an appropriate parametric, nonparametric, or semi-parametric survival analysis method. An ANOVA model may be utilized and tabulated along with the CIs. During the analysis, if a possible confounding variable was identified, the variable will be measured and entered into the analysis as a covariate.

Confounding factors that may impact tacrolimus response include race, age, and disease characteristics. It is possible that there may be differences in baseline demographics and disease states between the pharmacogenomic and control group. To minimize the potential impact of confounding variables on treatment response, an overall matching strategy has been incorporated into the design of the study. Please see [Section 8.4](#) for more information regarding the matching strategy.

The exploratory endpoints will be analyzed using descriptive statistics. No formal statistical testing is planned at this time.

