ATTACHMENT 1: Adverse Event Assessment Form:

Research adverse events as of @ ID@					
Adverse event (AE) history			Resolved		
AEs reported at previous visit			YES	NO	
1					
2					
3					
4					
5					

Since last visit, does patient have	Tac Dose Modification					NOTES
	YES	NO	Increase	Decrease	No Change	
1 Neurotoxicity (tremor, paresthesias, tingling, seizures, or headache)						
2 Nephrotoxicity related to tacrolimus						
3 Diarrhea, constipation						
4 Peripheral edema						
5 Hypertension						
6 Hyperglycemia						
7 Other adverse events						
8	

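### eGFR enters the secondary endpoints only as impairment bands, which also go to Kaplan-Meier, where a named eGFR comparison would be more sensitive; separately, the last two BPAR windows overlap

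*Combined protocol and SAP*

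**What the plan says.** **Renal endpoint.** Section 3.2 names the outcome as "Incidence of acute and chronic renal impairment. Renal function will be assessed using estimated Glomerular Filtration Rate (eGFR"). It continues "Patients will be categorized as having either mild" (eGFR 60-89 mL/min/1.73m²), moderate (30-59) or severe (below 30). It does not separate acute from chronic impairment.

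**Renal analysis.** Section 8.3, repeated in the study summary, states: "The incidence of an adverse outcome (ie, graft rejection, graft loss, renal impairment, tacrolimus toxicities, and death) will be estimated using Kaplan-Meier curves". Two generic rules in 8.3 could also apply. One begins "Categorical data will be compared using" and names the chi-square and Fisher's exact tests. The other reads "Continuous variables will be compared using the Wilcoxon test or the t-test". Neither is assigned to eGFR or to its bands.

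**Data.** Table 1 schedules eGFR at Day 0, Day 1 and every follow-up to 12 months. Section 4.1 asks for matching time points in the controls. The adverse event form (Attachment 1) has a separate yes/no item, "Nephrotoxicity related to tacrolimus".

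**Rejection endpoint.** Section 3.2 lists "The incidence of BPAR within the first 3 months, 3-6 months, 6-9 months, and 6-12 months after transplantation".

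**The concern.** Section 2.1 gives the two-sided risk that motivates the study: "low drug exposure increases risk to kidney rejection and high doses correlate with nephrotoxicity". Renal function is therefore a main safety outcome, and eGFR is its graded measure.

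Three features of the plan work against it:

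- Cutting eGFR into bands of about 30 units discards differences within a band. An unordered chi-square test then also ignores the order of the bands.
- Kaplan-Meier needs an onset. Section 2.1 describes transplantation as treatment for end-stage renal disease, so a recipient's Day 0 eGFR is expected to lie in an impairment band already. Entering a band is then not an onset unless a post-transplant event is defined.
- The BPAR windows do not divide the year. A reader who adds them up counts months 6-9 twice and finds no figure for months 9-12.

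The cost would be a less sensitive renal comparison and a rejection table that cannot be read as a sequence. The primary endpoint and its sample size are not touched.

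**Working it through.** **1. The plan's own figure.** Section 8.2 gives 130 per group for 40% against 60%, two-sided 5%, 90% power:

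n = [1.960·√(2·0.5·0.5) + 1.2816·√(0.24 + 0.24)]² / 0.20² = (1.3859 + 0.8879)² / 0.04 = 129.3, so 130 per group and 260 in total.

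This reproduces. It concerns the primary endpoint only. The documents give no mean, SD, difference or power for eGFR.

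**2. Inputs for the illustration.** From the documents: n = 130 per group, two-sided 5%, and the band limits. Assumed: normal eGFR at Month 12, control mean 45-65, SD (σ) 15-20, true difference d of 2, 3.5 or 7 mL/min/1.73m². Bands are cut at 29.5, 59.5 and 89.5, with 90 or above counted as no impairment.

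**3. Formulas.**

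- Wilcoxon: λ = √(3/π)·d / (σ√(2/130)); power = Φ(λ − 1.96) + Φ(−λ − 1.96).
- Chi-square on four categories: noncentrality = 130·Σ(p − q)²/(p + q), 3 degrees of freedom, where p and q are the band proportions in the two groups.

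**4. One case in full: mean 55, SD 20, d = 3.5.**

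- Wilcoxon: λ = 0.977 × 3.5/(20 × 0.1240) = 1.38; power 28%.
- Bands, severe / moderate / mild / none: control 10.1 / 48.8 / 36.9 / 4.2%; the other group 7.4 / 44.6 / 41.9 / 6.1%. Noncentrality = 130 × (0.00417 + 0.00189 + 0.00317 + 0.00350) = 1.66; power 16-17%.

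**5. Simulated power over the assumed range (means 45-65, SD 15-20).**

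| True difference | Wilcoxon on eGFR | Chi-square on bands | Gain, points |
|---|---|---|---|
| 2 | 12-19% | 6-10% | about 4-10 |
| 3.5 | 28-45% | 15-26% | 10-21 |
| 7 | 76-96% | 55-82% | 15-24 |

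The Wilcoxon formula gives 12-18%, 28-45% and 79-96%. The chi-square formula gives 8-11%, 16-25% and 55-77%. Simulated chi-square power can exceed the formula at mean 45, SD 15, where the top category is often empty and the test then has fewer degrees of freedom. At 7 units, a rank test on the same bands has 71-90%.

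**6. Which difference is plausible.** Sections 6.2 and 7.3 confine the intervention to the initial dose. Nonexpressers start on 0.1 mg/kg/day, which Section 4.3 also gives as standard dosing for prospective controls. Section 8.2 assumes about 50% *3/*3. If historical controls also started on that dose (an assumption), only about half the pharmacogenomic group starts differently. A group difference of 7 then needs 7/0.5 = 14 units in expressers, 3.5 needs 7, and 2 needs 4. So 7 is optimistic.

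**7. BPAR windows.** The listed windows last 3 + 3 + 3 + 6 = 15 months within a 12-month follow-up. A rejection at month 7 falls in both of the last two. Subtracting the 6-9 count from the 6-12 count does not give the 9-12 incidence: a patient with episodes in both parts appears once in each count and so drops out of the difference.

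**The case against.** The strongest reply is that 8.3 already permits what is asked. Its rule for continuous variables can be applied to eGFR, just as its rule for categories can be applied to the bands. This stands: a continuous comparison is not excluded. But no endpoint names one, and the only analysis that mentions renal impairment by name is the Kaplan-Meier estimate.

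A second reply is that most of the gain comes from respecting the order of the bands. This also stands. At 7 units, Wilcoxon on eGFR adds only about 5-7 points to a rank test on the bands. That is why the fix includes both.

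A third is that at small differences no analysis is well powered. True: at 2 units even Wilcoxon stays below 20%. The gain is real but modest.

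Two stronger readings are tempting and are not supported:

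- A reader might infer that the Kaplan-Meier analysis is a log-rank test on the first eGFR of 89 or below, with nearly everyone an event and almost no power. The plan names neither that event nor that test; it says only that incidence will be estimated. No power figure is given for it here.
- A reader might infer that patients at 90 or above are left unclassified. The bands grade impairment, so these patients simply have none.

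Renal harm is also not lost from the study, since the adverse event form records tacrolimus nephrotoxicity.

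On BPAR, the overlap may be a typing slip, and Kaplan-Meier for graft rejection gives a related cumulative estimate. The listed windows are still wrong as they stand.

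**Conclusion.** The point holds at a moderate size, for secondary endpoints only.

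- **Renal function: a cheap improvement.** Section 3.2 uses eGFR only to form bands, and band-based impairment does not suit Kaplan-Meier without a defined post-transplant event. The missing event rule alone would be missing detail. What makes the point worth acting on is that a better analysis of data already collected is available. Wilcoxon on eGFR beats chi-square on the bands at every difference examined, by about 4-10 points at 2 units and 15-24 at 7. These sizes rest on assumed means, SDs and differences and on normality, with no allowance for missing values. The larger gain needs a difference that looks optimistic when only the initial dose changes.
- **BPAR windows: wrong as written.** This needs no assumption. The order of the first three windows suggests that 9-12 months was meant, but only the authors can confirm it.

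**What to change.** 1. **Section 3.2:** name eGFR at 12 months as a continuous secondary outcome, with the other scheduled post-transplant visits as supporting time points. **Section 8.3:** state that it is compared by the Wilcoxon test.
2. If the bands are also compared, use an ordinal rank test in place of an unordered chi-square test, with 90 or above counted as no impairment.
3. In 8.3 and the study summary, take eGFR-band impairment off the Kaplan-Meier list, unless a post-transplant event is defined (threshold, earliest eligible time, confirmation, acute against chronic).
4. State a rule for eGFR that is missing after death or graft loss, and add a sensitivity analysis. This is the main downside of the change.
5. Change the last BPAR window to 9-12 months, subject to the authors' confirmation, and report cumulative 12-month BPAR separately.

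The cost is wording and a little analysis time. No new data are needed, because Table 1 already schedules eGFR at every visit and Section 4.1 requires matching control time points. The change does not address confounding in this non-randomised comparison.

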3.3 Exploratory Endpoints

The exploratory endpoints relate to the secondary objective of this study and are described below.

- Direct and indirect cost related to treatment and management kidney transplant recipients

4 Study Design

4.1 General Design

This is a single-center study of pharmacogenomic-guided tacrolimus dosing and drug monitoring in kidney transplant recipients (Figure 1). The pharmacogenomic group will partake in a 12-month study comprising of two periods, Genotype-Guided Initial Dosing Intervention and Follow-up.

Following screening, acquisition of consent, and genotyping, a comprehensive medical chart review will be conducted for the control group. Twelve-month post-transplant data will be collected in the control group with timepoints that match with the pharmacogenomics group.

Figure 1: Study Design

[figure not shown]

Figure 1. This figure provides the general study design for the study, which comprises of the Screening and two study periods (Intervention and Follow-up) for the pharmacogenomic group. After consent and genotyping have been conducted, a comprehensive medical chart review will be conducted for the control group.

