4.2 Rationale

Due to cost, time constraints, and limited patient population (there are approximately 80 kidney transplant recipients at UNC-CH), we are not able to conduct the ideal randomized, double-blind, two-group parallel study. Rather, we are proposing a study design that is practical, given the available resources and still investigates the safety and effectiveness of using genotype-guided tacrolimus dosing.

In this study, a comparison of the primary and secondary endpoints will be conducted between kidney transplant recipients who underwent prospective pharmacogenomic-guided tacrolimus dosing strategy (pharmacogenomic group) and patients who received standard tacrolimus dosing regimen historically and prospectively (control group). Although genotyping the control group can be more expensive and time consuming, knowing the genotype information of the control group will allow us to do the following: 1) identify if the control and pharmacogenomic groups are comparable with regards to genotype; and 2) conduct a subgroup analysis based on treatment and genotype, comparing the outcomes and tacrolimus levels of patients who are *CYP3A5*1/*1*, *CYP3A5*1/*3*, or *CYP3A5*3/*3* who received standard therapy versus genotype-guided dosing.

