6.2 Treatment Regimen

All patients who consented will undergo genotype testing prior to transplant. The genotype-guided dosing recommendation as shown in **Figure 3** below only refers to the initial tacrolimus dose. Subsequent tacrolimus dosing will then be adjusted according to trough concentrations and desired therapeutic concentrations. Therapy for oral tacrolimus will be prescribed by the kidney transplant team as part of a standard immunosuppression agent given to kidney transplant recipients starting at 0.1 mg/kg/day (nonexpressers) or 0.2 mg/kg/day (expressers) given in 2 divided doses; maximum total daily dose of tacrolimus is 20 mg/day.

As the drug and the doses being used are not investigational, tacrolimus will be stored and dispensed in accordance to current UNC-CH pharmacy procedures. The patients and investigators will not be blinded in the study, hence there will be no procedure related to blinding of study drug.

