8.4 Matching Strategy

As there are confounding variables, including age, race and disease state that may impact the results of the study, our study design incorporates an overall matching strategy, so that we can identify a well-matched control group. First, to control for differences in care over time, patients in the pharmacogenomic group will be matched to controls enrolled from 2010 to present. This time period was selected as there had been no major changes in standard of care or treatment regimen since 2010. After eligibility is met, control patients will be selected to match the pharmacogenomic group using a computerized matching algorithm that has been optimized to match baseline demographic and disease characteristics that have been identified a priori as likely to influence the treatment response to tacrolimus. To balance the trade-off between minimizing bias and maximizing matched sample size, a systematic approach will be conducted to identify the number of matched control patients for each patient in the pharmacogenomic group. This approach will include the following steps: 1) run the desired matching algorithm, starting with 1:1 (one control to one patient in the pharmacogenomic group) matching and iterating until the maximum desired number of potential controls per treated subject is reached; 2) for each iteration, test for covariate balance; and 3) generate numeric summaries and graphical plots of the balance statistics across all iterations in order to determine the optimal number (Linden and Samuels 2013).

The selection of patients for the control group using a matching algorithm will be conducted by an independent statistician in a blinded and unbiased manner. The statistician will have no knowledge of survival outcome, other outcome data, and genotype.

9 Safety and Adverse Events

Safety will be assessed throughout the study by evaluating physical exam, clinical chemistry, urinalysis, hematology, renal function, and incidence of adverse events (ie, graft rejection, graft loss, renal impairment, drug-related adverse events, tacrolimus toxicities, and death).

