9.5 Interim Analysis

An interim analysis will be performed on the primary endpoint when 30% of eligible patients have been enrolled and have completed the 6 months follow-up. The interim analysis will be performed by an independent statistician who is blinded for the subjects' treatment allocation.

Some of the questions that will be evaluated during the interim analysis will include:

- Is there an unexpectedly high rate of severe or life-threatening adverse events?
- Is the outcome of the trial treatment comparable with that of previous studies?

- Do the results of the interim analysis prove statistically significant differences between the trial treatments that exceed the differences defined by the statistical guidelines of the trial?

10 Data Handling and Record Keeping

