10.4.1.2 Genetic Data

There will be two types of genetic data: 1) genotype data related to tacrolimus dosing, which includes primary genotype data required for the dosing algorithms and 2) other genetic data that will be used for additional, ancillary analyses. The data unrelated to the dosing algorithms will be derived from the stored buccal swab sample at the Central Laboratory (CL) and are not required for the clinical trial itself. As such, they are not discussed further in this protocol. The first (genotype data required for the dosing algorithm) will be assayed at CGI under the strictest CLIA (Clinical Laboratory Improvement Amendment) standard for genotyping of human specimens. The other genotype/sequencing data will be used to define additional genetic determinants of tacrolimus dosing in patients who have disparate response from the genotype-guided dose.

Genotyping at the Central Laboratory. The CL will be responsible for: 1) extracting DNA from all participants' buccal swab samples and 2) storing DNA on all participants for future genotyping of other variants of other genes that may be important for assessing response to tacrolimus. For future studies, the CL will be responsible for developing a multiplex platform that can assay numerous genetic variants within one reaction.

Sample Collection for Storage and Analyses in Central Laboratory. Following acquisition of informed consent, buccal swab samples will be collected per manufacturer's directions. Using DNA isolation kits suitable for buccal swab samples, DNA will be isolated at the CL according to the manufacturer's instructions. A third of the aliquot will be retained by the CL, and the remainder will be delivered to CGI in a chilled insulated container. The DNA samples will be stored in barcoded tubes at the CL. All DNA samples that will be sent to CGI will also be in barcoded tubes, so that laboratory personnel at CGI are blinded to the patient's identity. All samples will be tracked using the barcode and tracking system.

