10.4.2 Historical Data

Historical data from the control group will be obtained from 2010 until the end of study period. The historical controls will consist of age- and disease-matched patients who met eligibility criteria and have had previously

received kidney transplantation with standard tacrolimus dosing. These patients will also be asked to give consent for genotyping during a standard routine follow-up visit post-transplantation. Eligible patients who consented will be included in the control group and their safety and efficacy data will be collected retrospectively for up to 12 months from the initiation of the first tacrolimus dose.

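### Historical controls' charts are to be reviewed after genotyping with no genotype blinding of abstractors, leaving judgement-based secondary outcomes open to avoidable expectation bias

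*Combined protocol and SAP*

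**What the plan says.** Section 4.1 gives the order of work for controls: "Following screening, acquisition of consent, and genotyping, a comprehensive medical chart review will be conducted for the control group". The Figure 1 legend says the same. For historical controls, section 10.4.2 adds that "their safety and efficacy data will be collected retrospectively for up to 12 months", counted from the first tacrolimus dose.

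Blinding appears in four places, and only one concerns knowledge of genotype:
- Section 8.4, on the statistician who selects matched controls: "The statistician will have no knowledge of survival outcome, other outcome data, and genotype".
- Section 9.5: the interim statistician is blind to treatment allocation. Genotype is not mentioned.
- Section 10.4.1.2: "laboratory personnel at CGI are blinded to the patient's identity". This does not bear on chart review.
- Section 6.2: "The patients and investigators will not be blinded in the study".

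No section says who abstracts the control charts or what they may see.

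Section 3 makes the relation of genotype to trough levels and clinical outcomes the primary objective. Sections 4.4 and 5.3 say that outcomes are to be compared between expressers and nonexpressers. Section 2.1 gives the expected direction: low exposure and rejection in expressers, toxicity in nonexpressers.

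**The concern.** In historical controls the whole outcome record exists before study genotyping, and genotype played no part in their treatment under this study. Abstraction therefore does not need the result. Section 4.2 wants control genotypes for a comparability check and for subgroup analysis, and both take place at analysis.

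Several outcomes require the abstractor to interpret notes. One secondary endpoint is "Proportion of patients who had dose adjustments and/or drug alteration or addition due to insufficient immunosuppression", which turns on the reason for a change. Tacrolimus toxicities (3.2) and the yes/no judgement of drug-relatedness (9.3.1) are similar. An abstractor who knows the genotype and the hypothesis may read an ambiguous note in the expected direction.

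Controls are also the patients in whom genotype did not set the starting dose, so they give the cleanest view of genotype against outcome. Section 8.4 protects the selection of controls from knowledge of genotype. The same protection is missing where their outcomes are classified.

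**Working it through.** **1. The plan's own figure.** Section 8.2: 40% v 60%, two-sided 5%, 90% power. Per group, n = [1.960·√(2·0.5·0.5) + 1.282·√(0.4·0.6 + 0.6·0.4)]² / 0.20² = (1.386 + 0.888)² / 0.04 = 129.3, so 130 per group and 260 in total. The stated size reproduces (power at 130 per group 90.2%). This point disputes no stated number.

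**2. Which outcomes are exposed.**
- Need judgement from notes: the reason for a dose or drug change, tacrolimus toxicities, and relatedness of an adverse event.
- Leave little room for judgement: trough in 8-10 ng/mL on Day 3 and Day 7 (primary), time to range, eGFR categories, biopsy-proven rejection, graft loss and death.

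**3. Size, as illustration only.** From the documents: 130 controls and about 50% *CYP3A5*3/*3* (8.2), so about 65 v 65. Assumed, and not in the documents: equal true event rates in both genotype groups, and the misclassification below.

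The rejection probability is the sum of Bin(x; 65, p₁)·Bin(y; 65, p₂) over all (x, y) with |z| > 1.960, where z = (x − y)/65 ÷ √[p̂(1 − p̂)·2/65] and p̂ = (x + y)/130.

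| Assumption | Observed rates | Rejects at 5% |
|---|---|---|
| True 20%, no misclassification | 20% v 20% | 4.9% |
| True 20%, 2.5 points each way | 17.5% v 22.5% | 10.7% |
| True 20%, 5 points each way | 15% v 25% | 29.4% |
| True 20-50%, capture 90% in both | 18-45% in both | 4.7-5.3% |
| True 20-50%, capture 90% v 80% | 18% v 16% to 45% v 40% | 5.8-8.8% |
| True 20-50%, capture 90% v 70% | 18% v 14% to 45% v 35% | 9.1-21.8% |

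In patients, 5 points is 0.05 × 65 = 3.25 per genotype group, and 2.5 points is 1.6. The 29.4% row is demanding: abstractors must discard a quarter (5/20) of true toxicities in expressers and add as many in nonexpressers.

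**4. Race stratification.** Section 8.3 allows a Cochran-Mantel-Haenszel correction for race in some comparisons. Take 65 patients per race (4.4 aims for equal numbers), *3 frequencies of 0.82-0.95 in Whites and 0.33 in African Americans (2.1, 4.4), and Hardy-Weinberg proportions (an assumption). Simulation without continuity correction (400,000 trials) then gives 14-20% for 15% v 25%, and 7-9% for 17.5% v 22.5%.

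**5. What hiding the result leaves in place.** Under the same assumptions, guessing nonexpresser for Whites and expresser for African Americans is right in ½[q² + (1 − 0.33²)] of patients. With q = 0.82 this is ½(0.672 + 0.891) = 78%; with q = 0.95 it is ½(0.9025 + 0.891) = 90%. Doses and troughs in the chart are further clues.

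**The case against.** **Exposure is inferred.** No section says that abstractors see genotype. The order in 4.1 may only mean that consent and swab come before access to records. The statement in 4.3 that results enter the electronic record is made for waitlisted patients, and the unblinded statement in 6.2 is made about study drug. This stands: the defect is a stated order with no safeguard, and a reader should not infer that the protocol describes an unblinded review.

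**The comparison is loosely specified.** Section 4.2 plans to "conduct a subgroup analysis based on treatment and genotype", which might be read as expresser v nonexpresser among controls. The sentence goes on to compare standard with guided dosing within genotype, so it does not support that reading. Section 3 likewise meets its objective by comparing the two groups, and 8.3 names no control-only genotype test. The support is the stated aim in 4.4 and 5.3, which is enough to justify protecting the classification.

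**The exposure is narrow.** Events in historical controls were recorded in routine care before study genotyping, so only later abstraction and classification are at risk. Attachment 1 asks about tacrolimus-related nephrotoxicity, but it is worded for visits and is not shown to be used retrospectively. This also stands.

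**A change of order is not a cure.** Prospective controls give swabs at enrolment and are followed for up to 12 months, while the result may reach the electronic record (4.3). In the pharmacogenomic group the starting dose reveals genotype. Race, doses and troughs remain visible for everyone. A reader might infer that reversing two steps eliminates the bias; the documents support only a reduction, in historical controls.

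**Conclusion.** The point holds within limits. The plan places historical-control chart review after genotyping without keeping genotype from the abstractor. This creates an avoidable risk of expectation bias in judgement-based secondary outcomes when expressers are compared with nonexpressers. It does not threaten the primary endpoint or the other laboratory-based or hard outcomes to any material degree.

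The size cannot be derived from the documents. The illustrated range of roughly 6-29%, against a nominal 5%, rests on assumed event rates and assumed misclassification, and race stratification lowers it. The upper figure should not be read as an estimate. The range does show that a shift of about two to three patients per genotype group is enough to matter.

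**What to change.** In section 4.1 and the Figure 1 legend, state that for historical controls outcome data are abstracted and locked after consent and before the genotype result is released to the study team. Hold genotype in a separate file and link it only at analysis. In section 8.3, record that historical-control outcomes were locked without knowledge of genotype, and that this does not extend to prospective controls or the pharmacogenomic group.

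Sample size, power, alpha, visits and treatment are unchanged. The cost is some sequencing and data-lock work, plus a few charts abstracted for patients whose genotyping later fails. The change should be made before control abstraction begins, because charts already classified with genotype known are hard to recover.
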